4.4. Safety Analysis Set

Safety Analysis Set (SafAS) will consist of all participants who received nirsevimab in the study and all randomized participants who were randomized to the no intervention group and did not receive nirsevimab inadvertently.

SafAS participants are analyzed according to the study intervention they actually received.

5. Data Handling

5.1. Time Points and Visit Windows

5.1.1. General Definitions

All assessment days will be related to Day 1. Day 1 is the date of randomization (for no intervention group) / immunization (for nirsevimab group).

Relative days after Day 1 are calculated as (assessment date – Day 1 date) + 1. Relative days prior to Day 1 are calculated as (assessment date – Day 1 date). The day prior to Day 1 is Day -1. Day 0 is not defined.

The date of the immunization for each participant in the nirsevimab group will be taken from the Immunization eCRF page. If the date on this eCRF page is missing, alternatively the date of randomization will be used.

The date of the randomization for each participant in the no intervention group will be taken from the Randomization eCRF page. If the date in this eCRF page is missing, alternatively the date of informed consent (Informed Consent Date eCFR page) will be used.

5.1.2. Screening Period

For all participants, the screening period is defined as the period from informed consent to Day 1. For some variables, data from more than one assessment within the screening period can be collected prior to randomization (for no intervention group) / immunization (for nirsevimab group).

The baseline value for a variable is therefore defined as the last non-missing value collected before Day 1 in the screening period.

5.1.3. Treatment Period

At the time of Primary Analysis, the Treatment Period is defined as the period from the date / time of randomization (for no intervention group) / immunization (for nirsevimab group) up to and including:

- The cut-off date for the Primary Analysis,
- Lost to follow-up or consent withdrawal date, if participant is lost to follow-up or withdraws consent.

At the time of First Year Analysis, the Treatment Period is defined as the period from the date / time of randomization (for no intervention group) / immunization (for nirsevimab group) up to and including:

- The date of 12-month safety follow-up call, if 12-month safety follow-up call occurs before or on Day 1 + 365 + 14,
- Day 1 + 365 + 14 date, if 12-month safety follow-up call occurs after Day 1 + 365 + 14,
- Lost to follow-up or consent withdrawal date, if participant is lost to follow-up or withdraws consent.

At the time of Second Year Analysis, the Treatment Period “from Day 1 to 366 Days Post-Dosing/Randomization” for UK reconsented participants is defined as the period from the date / time of randomization (for no intervention group) / immunization (for nirsevimab group) up to and including:

- The date of 12-month safety follow-up, if 12-month safety follow-up call occurs before or on Day 1 + 365 + 14,
- Day 1 + 365 + 14 date, if 12-month safety follow-up call occurs after Day 1 + 365 + 14
- The date of 24-month safety follow-up or until lost to follow-up or consent withdrawal

At the time of Second Year Analysis, the Treatment Period “from 366 Days Post-Dosing/Randomization to 731 Days Post-Dosing Randomization” for UK reconsented participants who are not lost to follow-up or who don’t withdraw consent before 366 Days Post-Dosing/Randomization is defined as the period from:

- The date of 12-month safety follow-up + 1, if 12-month safety follow-up call occurs before or on Day 1 + 365 + 14,
- Day 1 + 365 + 14 + 1 date, if 12-month safety follow-up call occurs after Day 1 + 365 + 14

Up to and including:

- The date of 24-month safety follow-up call, if 24-month safety follow-up call occurs before or on Day 1 + 730 + 14,
- Day 1 + 730 + 14 date, if 24-month safety follow-up call occurs after Day 1 + 730 + 14,
- Lost to follow-up or consent withdrawal date, if participant is lost to follow-up or withdraws consent.

At the time of Second Year Analysis, the Treatment Period “from Day 1 to 731 Days Post-Dosing/Randomization” for UK reconsented participants is defined as the period from the date / time of randomization (for no intervention group) / immunization (for nirsevimab group) up to and including:

- The date of 24-month safety follow-up call, if 24-month safety follow-up call occurs before or on Day 1 + 730 + 14,
- Day 1 + 730 + 14 date, if 24-month safety follow-up call occurs after Day 1 + 730 + 14,
- Lost to follow-up or consent withdrawal date, if participant is lost to follow-up or withdraws consent.

Data collected at Day 1 will be assigned to the Treatment Period unless the time (HH:MM) of data collection and time (HH:MM) of randomization (for no intervention group) / immunization (for nirsevimab group) are both recorded and the data collection time is before the time of randomization (for no intervention group) / immunization (for nirsevimab group). In this case, the assessment will be assigned to the screening period. If the time (HH:MM) of data collection is not recorded but the protocol and / or eCRF includes an instruction to the effect that all Day 1 assessment are to be performed prior to the randomization (for no intervention group) / immunization (for nirsevimab group), the data collected at Day 1 will be assigned to the screening period. However, adverse events and medications starting on Day 1, will be assigned to the Treatment Period.

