- ** From D366 to D731, UK reconsented participants' parents/LARs are requested to capture in a memory aid any hospitalizations and emergency-room visits experienced by the participants. The memory aid will be reviewed by the investigator or site staff during the 18-month and 24 month follow-up calls to collect any information on SAE or LRTI hospitalizations that may have occurred since the previous contact. If an SAE is reported, the investigator or site staff will assess the relationship and only related SAE will be reported in the eCRF.
- †† Immediate AE occurring within 30 minutes after immunization will be collected on V01.
- Assessment of LRTI (inpatient) requiring hospitalization. In case of hospitalization due to LRTI symptoms at any time during the study after randomization, an RSV test is to be performed as per the hospital routine practice. Test results and information about the LRTI hospitalization such as O2 saturation, respiratory rate, oxygen supplementation, intravenous fluid administration, admission to intensive care unit, date of admission and of discharge are to be collected retrospectively.
 - It is to be noted that, for participants hospitalized due to LRTI symptoms whose participation in the study is prematurely terminated, the Investigator or designee may seek information on the LRTI hospitalization for the assessment of efficacy endpoints. This retrospective collection of information on LRTI hospitalization for participants withdrawn from the study will be possible only if the parents or LARs provided consent by ticking the corresponding box in the informed consent form.
- A safety follow-up phone contact is to be made at 12 months post-dosing/randomization. For participants who have prematurely terminated the study (eg, no answer to monthly electronic contact within the first 6 months post-dosing/randomization), the site or authorized designee should attempt to contact them and complete this 12-month safety follow-up to identify the occurrence of any SAEs, MAAEs, and AESIs that had not yet been reported, except if they specified that they do not want to be contacted again and it is documented in the source document.

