7.2 Participant Discontinuation/Withdrawal from the Study

- A participant may be withdrawn from the study at any time at her/his parents or LARs request or may be withdrawn at any time at the discretion of the investigator for safety, behavioral, or compliance reasons. This is expected to be uncommon.
- The reason for withdrawal should be clearly documented in the source documents and in the eCRF: Adverse Event, Lost to Follow-up, Protocol Deviation, or Withdrawal by Parents or LARs.
- For participants hospitalized due to a LRTI symptoms who are withdrawn from the study, the Investigator or designee may seek information from the facility where medical attention was sought to complete the participant's eCRF and assess the case. This retrospective collection of information on LRTI hospitalization for participants withdrawn from the study will be possible only if the parents or LARs provided consent by ticking the corresponding box in the informed consent form.
- The participant will be permanently discontinued from the study at that time.
- If the parents or LARs of the participant withdraw consent for disclosure of future information, the Sponsor may retain and continue to use any data collected before such a withdrawal of consent.
- Withdrawn participants will not be replaced.

Follow-up of Discontinuations

For participants who have prematurely terminated the study, the site should attempt to contact their parents or LARs and complete all scheduled safety follow-ups, except if they specified that they do not want to be contacted again and it is documented in the source document.

For participants where the reason for early termination is lost to follow-up, the site will not attempt to obtain further safety information after last contact attempt on the 12-month follow-up for France, Germany, and UK non-reconsented participants and on the 24-month follow-up for UK reconsented participants. See Section 7.3 for definition of "lost to follow-up".

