6.7.2. Adverse Events

6.7.2.1. Definitions/ Derivations

All AEs recorded on the eCRF will be coded using the MedDRA dictionary (version 25.0) and classified as treatment-emergent AEs (TEAEs) as follows:

- Pre-treatment AEs are events
 - that start prior to the start of the Treatment Period and with a stop date before the Treatment Period
- or
- with a stop date after the start of the Treatment Period or with a missing stop date, but with a grade lower or equal to 1.
- TEAEs are either events
 - with the start date and time posterior to the start of the Treatment Period and up to the end of the Treatment Period

or

- events with the start date and time prior to the start of the Treatment Period
 - whose severity is greater than 1 or missing
- and
 - stop date is missing or not before the Treatment Period.
- Treatment-Emergent Serious AEs will be defined as TEAEs where Serious = “Yes”
- The relationship between a TEAE and treatment is assessed as related, or not related. A treatment-related TEAE will be defined as a TEAE considered by the investigator as related or, with unknown / missing relationship to treatment for participants who received nirsevimab on Day 1. An unknown / missing relationship between a TEAE and treatment for participants who received no intervention will be considered as not related.
- Assessment of AE intensity will be based on the AEs intensity grading scales adapted from the “FDA Guidance for Industry: Toxicity Grading Scale for Healthy Adult and Adolescent Volunteers Enrolled in Preventive Vaccine Clinical Trials, September 2007”
- TEAEs leading to discontinuation of study are defined as TEAEs where “Caused Study Discontinuation” is indicated as “Yes”.
- Pyrexia includes those adverse events with PT term equal to ‘Pyrexia’.
- Injection site reactions include those adverse events with category of adverse event equal to ‘IMP Injection/Administration Site Reaction’ or ‘Other Vaccination Injection/Administration Site Reaction’.
- Rash includes those adverse events with PT term equal to ‘Erythema’, ‘Rash’, ‘Rash macular’, ‘Rash maculo-papular’ or ‘Urticaria’.

In addition to the aforementioned AE types, TEAEs of special interest will be identified in eCRF (Is the event an AESI = Yes):

- Hypersensitivity, including anaphylaxis
- Immune complex disease
- Thrombocytopenia

Immediate AEs are recorded to capture medically relevant AEs which occur within the first 30 minutes after immunization.

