PT. TEAEs with missing intensity will be included in the counts of the ‘Number of Participants with at least one TEAE’, ‘System Organ Class’, and ‘Preferred Term’ rows of the summary but they will not be included in the counts by intensity.

In addition, all AE tables by SOC and PT flagged with (#) as well as the summary table will be repeated in participants who received Beyfortus as a routine medication if there are at least 10 concerned participants.

Summaries by SOCs and PTs will be sorted by SOCs by their Internationally Agreed Order (MedDRA) and PTs within SOC by descending order of total incidence. Where preferred terms tie PTs will be sorted alphabetically.

No statistical comparisons of AEs between treatment groups will be performed.

All AE data will be listed and Pre-treatment AEs and TEAEs will be presented together. Treatment-emergence status will be flagged in the listing. The listing will present the relative start and stop day of the AE calculated relative to the first dose of treatment and will be presented for those participants who received at least one dose of treatment. If the AE is “Ongoing” it will be indicated as such in the listing and the relative stop day will not be calculated. Only original dates will be presented in the listing even though the relative day may be based on an imputed date.

In addition, the following listings will be presented:

- Listing of Deaths
- Listing of Serious TEAEs
- Listing of TEAEs Leading to Discontinuation of Study
- Listing of TEAEs of Special Interest
- Listing of Immediate TEAEs reported in the 30 minutes after immunization
- Listing of Medically Attended AEs
- Listing of all non TEAEs not included in the Safety Analysis
- Listing of all non TEAEs not included in the Safety Analysis in the United Kingdom for Reconsented Participants (only at the time for the Second Year Analysis)
- Listing of all Adverse Events starting before the End of the Treatment Period defined for the First Year Analysis but not included in the First Year Analysis since they were reported after First Year Database Lock in the United Kingdom for Reconsented Participants (only at the time for the Second Year Analysis)

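### SAP 5.1.3: the UK Day 1 to 366 safety period carries a 24-month end date, and consent withdrawal ends the Treatment Period without separating families who still allow safety contact

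*SAP*

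**What the plan says.** **UK first-year period.** For the Second Year Analysis, SAP 5.1.3 defines a Day 1 to 366 period for UK reconsented participants. Its first two end points are the 12-month call date and a cap at Day 1 + 365 + 14. The third is "The date of 24-month safety follow-up or until lost to follow-up or consent withdrawal", with no condition attached. A separate Day 1 to 731 period follows. SAP 6.7.2.2 produces the related serious TEAE tables and the TEAE summary table for Day 1 to 366, Day 366 to 731 and Day 1 to 731.

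**Withdrawal.** In the Primary Analysis, First Year and other Second Year periods, one end point is "Lost to follow-up or consent withdrawal date, if participant is lost to follow-up or withdraws consent". No rule says which end point governs when more than one applies.

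**TEAE definition.** SAP 6.7.2.1 classes as treatment-emergent those events "with the start date and time posterior to the start of the Treatment Period and up to the end of the Treatment Period". A further branch covers events already present before the period starts, which is not at issue here.

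**Protocol collection.** For infants who ended the study early, Protocol 7.2 says "the site should attempt to contact their parents or LARs and complete all scheduled safety follow-ups". The only exception is a documented refusal of further contact. The Schedule of Activities footnote says the site or designee "should attempt to contact them and complete this 12-month safety follow-up to identify the occurrence of any SAEs, MAAEs, and AESIs" not yet reported.

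**Efficacy side.** SAP Table 2 treats withdrawing consent from further data collection and ending the study early without doing so as two separate intercurrent events. It also states an earliest-of censoring rule.

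**The concern.** Both faults can put an event in the wrong place if the rules are programmed as written.

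The stray 24-month end point undermines the split between first and second year. The extension was added for a post-marketing commitment on second-season disease enhancement (Protocol 10.6), so the year of onset of a related SAE matters.

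The withdrawal rule may discard from the main tables safety data that the protocol tells sites to obtain and that families have not refused to give. SAP 6.1 uses the number of participants in the analysis population as the default denominator for percentages, not exposure time. An infant whose period is cut short therefore still counts fully in the denominator, while a later event does not count in the numerator. The overview, the SOC/PT tables and the registry SAE tables in SAP 6.9 are all built on TEAEs. For rare SAEs and AESIs, a few missing events would be visible.

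**Working it through.** **1. Reproduce the SAP's own bounds.** SAP 5.1.1 gives relative day = (date − Day 1) + 1.
- Day 1 + 365 + 14: 379 + 1 = Day 380.
- Day 1 + 730 + 14: 744 + 1 = Day 745.

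Both match SAP Table 5. Without the 14-day allowance, the calls fall on Day 366 and Day 731.

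**2. Length of the UK first-year period.**

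| End point applied | Period ends |
|---|---|
| 12-month call or its cap | Day 366-380 |
| 24-month bullet, call made in its window | Day 731-745 |

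The difference is 731 − 366 = 745 − 380 = 365 days. Across the call windows it ranges from 731 − 380 = 351 to 745 − 366 = 379 days. With the 24-month bullet in force, the period coincides with the Day 1 to 731 period. It also overlaps the Day 366 to 731 period, which SAP 5.1.3 starts on the day after the 12-month end date.

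**3. Path of a post-withdrawal event.** Take an infant whose parents withdraw on Day 181, do not refuse contact, and report at the 12-month call an SAE that began on Day 250.
- Protocol 7.2 and the Schedule of Activities footnote: the event is sought.
- SAP 5.1.3, withdrawal bullet: the period ended on Day 181. SAP 5.1.3, call-date bullet: it ended at the call. No rule chooses.
- SAP 6.7.2.1: under the withdrawal date the event is not a TEAE; under the call date it is.
- SAP 6.7.2.2: if it is not a TEAE, it leaves the overview and the SOC/PT tables. It stays in the listing of all AE data, which flags treatment-emergence, and in "Listing of all non TEAEs not included in the Safety Analysis". A death would also remain in the summary by primary cause and in the listing of deaths.

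**4. Follow-up cut per infant.** Withdrawal on Day d removes 366 − d days of the SAE/MAAE/AESI window: 335 days for Day 31, 185 for Day 181 and 95 for Day 271.

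**5. Size, by assumption only.** The documents give no withdrawal rate, share still contactable, or SAE rate. With N = 14,430 planned per arm (Protocol 9.2), withdrawal proportion w, contactable share c, a mean of 183 days cut and SAE rate r per person-year:

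SAEs outside the TEAE tables per arm = N × w × c × (183/365.25) × r

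| w | c | Infants | Person-years | SAEs at r = 0.02 | SAEs at r = 0.05 |
|---|---|---|---|---|---|
| any | 0 | 0 | 0 | 0 | 0 |
| 1% | 50% | 72 | 36.1 | 0.7 | 1.8 |
| 3% | 50% | 216 | 108.4 | 2.2 | 5.4 |
| 5% | 100% | 722 | 361.5 | 7.2 | 18.1 |

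The range is 0 to about 18 per arm. Every input except N is assumed.

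**The case against.** **The term may already mean refusal of data.** If consent withdrawal in SAP 5.1.3 carries the Table 2 meaning, no later data should exist and the second fault largely disappears. This is the strongest counter-argument, and it cannot be excluded. But 5.1.3 omits the Table 2 qualifier, and the discontinuation reason in SAP 6.2 is simply withdrawal by parent or guardian. Protocol 7.2 also lists that reason separately from withdrawing consent to disclosure of future information. The term needs defining either way.

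**The affected group is narrow.** This stands. Discontinuation recorded as an adverse event or protocol deviation does not trigger the bullet. Under Protocol 7.3, loss to follow-up is declared only at the 12- or 24-month call, so little is cut there unless the date is set back to the last contact. What remains is parental withdrawal with contact still allowed.

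**Stronger readings the documents do not support.**
- A reader might infer that these events vanish from every safety output. They do not: the deaths-by-cause summary is not restricted to TEAEs, and several listings keep the events.
- A reader might infer that exclusion is certain. It is not: the call-date bullet could equally be applied.
- A reader might infer that risk on nirsevimab is understated relative to control. SAP 6.6.2.2 raises only the possibility of excess withdrawals, and in the no-intervention group. Truncation would then remove more control events. SAP 6.7.2.2 also plans no statistical comparison of AEs between groups.

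**The 24-month bullet looks like a drafting remnant.** Probably so: the label and the start of the next period show the intended end. SAP 6.7.2.2 also deliberately carries first-year events still ongoing at Day 366 into the second-year summary, so some double appearance is by design. That does not cover the reverse case of a second-year onset in a first-year table. Only related SAEs are collected in year two, which limits the number.

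**Conclusion.** Both faults hold. The UK Day 1 to 366 period has an end point that contradicts its label by about a year (351 to 379 days) and, applied as written, duplicates the Day 1 to 731 period. The consent-withdrawal end point is undefined and has no precedence rule, so SAEs, MAAEs and AESIs properly collected from withdrawn but contactable infants can be left out of the TEAE-based tables.

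The second conclusion rests on two conditions: that some families withdraw while still allowing contact, which the protocol provides for, and that the programmer applies the withdrawal date. The number of events cannot be derived from the documents and may be zero; the assumed ranges give at most about 18 SAEs per arm. The direction of any between-arm effect is open. Since the stated rules can give a wrong or contradictory assignment when followed, this is more than a missing detail.

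**What to change.** In SAP 5.1.3:
1. In the UK Day 1 to 366 definition, replace the 24-month bullet with the loss-to-follow-up/withdrawal bullet used for the other periods.
2. Define consent withdrawal as in Table 2, and end the period at that date only where consent to further data collection was withdrawn.
3. For other early terminations, end the period at the last safety contact, capped at Day 1 + 365 + 14, or Day 1 + 730 + 14 for the periods that run to 24 months.
4. With item 3 in place, state in every definition that the earliest applicable end date governs.

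No new data collection is needed: the protocol already seeks these events, and Table 2 already requires early leavers to be classified by consent to further data collection. The cost is SAP wording plus possible regeneration of affected safety tables. SAP version 6.0 is dated January 2025, and section 7 describes the re-run at the First Year Analysis in the past tense, so first-year tables may already exist.

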5.1.4. Analysis Windows for monthly reporting of events via eDiary

[Table 5 Definition of Analysis Windows for monthly reporting of events of interest via eDiary](#) describes and provides the relative study day ranges to be applied to the date of event reporting by parents via eDiary to derive the analysis windows for monthly reporting of events of interest.

The following considerations are to be followed when deriving the analysis windows:

- The relative day number of the event reporting lies between the lower and upper boundary of the window (the boundary values are included)

Table 5 Definition of Analysis Windows for monthly reporting of events of interest via eDiary

	Analysis Window ^a
Month 1	Day 1 to 31
Month 2	Day 32 to 61
Month 3	Day 62 to 91
Month 4	Day 92 to 121
Month 5	Day 122 to 151
Month 6	Day 152 to 181
Month 7	Day 182 to 211
Month 8	Day 212 to 241
Month 9	Day 242 to 271
Month 10	Day 272 to 301
Month 11	Day 302 to 331
Month 12	Day 332 to 366 +14 days (From Day 332 to 380)
Month 18	Day 367 +14 to 546 +14 (From Day 381 to 560)
Month 24	Day 547 +14 to 745 (From Day 561 to 745)

^a Relative to randomization (for no intervention group) / immunization (for nirsevimab group)

